### **7.2.2.2 Events of Clinical Interest**

Selected non-serious and serious adverse events are also known as Events of Clinical Interest (ECI) and must be reported to the Sponsor.

For the time period beginning after documented informed consent is provided until treatment allocation/randomization, any ECI, or follow up to an ECI, that occurs to any subject must be reported within 24 hours to the Sponsor if it causes the subject to be excluded from the trial, or is the result of a protocol-specified intervention, including but not limited to washout or discontinuation of usual therapy, diet, placebo treatment or a procedure.

For the time period beginning at treatment allocation/randomization through 14 days following cessation of treatment, any ECI, or follow up to an ECI, whether or not related to the Sponsor's product, must be reported within 24 hours to the Sponsor, either by electronic media or paper. Electronic reporting procedures can be found in the EDC data entry guidelines. Paper reporting procedures can be found in the Investigator Trial File Binder (or equivalent).

Events of clinical interest for this trial include:

1. an elevated AST or ALT lab value that is greater than or equal to 3X the upper limit of normal and an elevated total bilirubin lab value that is greater than or equal to 2X the upper limit of normal and, at the same time, an alkaline phosphatase lab value that is less than 2X the upper limit of normal, as determined by way of protocol-specified laboratory testing or unscheduled laboratory testing.\*

\*Note: These criteria are based upon available regulatory guidance documents. The purpose of the criteria is to specify a threshold of abnormal hepatic tests that may require an additional evaluation for an underlying etiology. The trial site guidance for assessment and follow up of these criteria can be found in the Investigator Trial File Binder (or equivalent).

2. Severe or serious cases of *C. difficile* infection such as toxic megacolon or pseudomembranous colitis.
3. Significant hematologic adverse events, defined as a clinically meaningful change in hemoglobin, platelet count, or absolute neutrophil count where one of these hematologic parameters reaches the following cutoff values by age ([Table 4](#)). For all subjects except preterm neonates, these cutoffs are based on Grade 2 low values as categorized in the US National Institutes of Health, Division of AIDS, AE grading scale for adults and children (version 2, 2014). For preterm neonates, clinically significant low values for these parameters are per local standards:

Table 4 Cutoff Values for Hematological Events of Clinical Interest by Age

Laboratory Test by Age Group	Cutoff Value
Hemoglobin	
57 days to <13 y	<9.5 g/dL
36-56 days	<8.5 g/dL
22-35 days	<9.5 g/dL
8 to 21 days	<11 g/dL
<8 days	<13 g/dL
Platelet Count	
Any age	<1 $\times$ 10  cells/mm 
Absolute Neutrophil Count	
>7 days	<800 cells/mm 
2-7 days	<1.250 $\times$ 10  cells/mm 
$\leq$ 1 day	<4.000 $\times$ 10  cells/mm 

4. Serotonin syndrome in subjects receiving drugs with serotonergic potential.

### 7.2.3 Evaluating Adverse Events

An investigator who is a qualified physician will evaluate all adverse events with respect to the elements outlined in [Table 5](#). The investigator's assessment of causality is required for each adverse event. Refer to [Table 5](#) for instructions in evaluating adverse events.

Table 5 Evaluating Adverse Events

Maximum Intensity	Mild	awareness of sign or symptom, but easily tolerated (for pediatric trials, awareness of symptom, but easily tolerated)
	Moderate	discomfort enough to cause interference with usual activity (for pediatric trials, definitely acting like something is wrong)
	Severe	incapacitating with inability to work or do usual activity (for pediatric trials, extremely distressed or unable to do usual activities)
Seriousness	A serious adverse event (AE) is any adverse event occurring at any dose or during any use of Sponsor's product that:	
	† Results in death; or	
	† Is life threatening; or places the subject, in the view of the investigator, at immediate risk of death from the event as it occurred [Note: This does not include an adverse event that, had it occurred in a more severe form, might have caused death.]; or	
	† Results in a persistent or significant disability/incapacity (substantial disruption of one's ability to conduct normal life functions); or	
	† Results in or prolongs an existing inpatient hospitalization (hospitalization is defined as an inpatient admission, regardless of length of stay, even if the hospitalization is a precautionary measure for continued observation. (Note: Hospitalization for an elective procedure to treat a pre-existing condition that has not worsened is not a serious adverse event. A pre-existing condition is a clinical condition that is diagnosed prior to the use of an MSD product and is documented in the patient's medical history.); or	
	† Is a congenital anomaly/birth defect (in offspring of subject taking the product regardless of time to diagnosis); or	
	Is a cancer (although not serious per ICH definition, is reportable to the Sponsor within 24 hours to meet certain local requirements); or	
	Overdose, although not serious per ICH definition, whether accidental or intentional, with or without an accompanying adverse event/serious adverse event, is reportable to the Sponsor within 24 hours to meet certain local requirements.	
	Other important medical events that may not result in death, not be life threatening, or not require hospitalization may be considered a serious adverse event when, based upon appropriate medical judgment, the event may jeopardize the subject and may require medical or surgical intervention to prevent one of the outcomes listed previously (designated above by a †).	
Duration	Record the start and stop dates of the adverse event. If less than 1 day, indicate the appropriate length of time and units	
Action taken	Did the adverse event cause the Sponsor's product to be discontinued?	
Relationship to Sponsor's Product	Did the Sponsor's product cause the adverse event? The determination of the likelihood that the Sponsor's product caused the adverse event will be provided by an investigator who is a qualified physician. The investigator's signed/dated initials on the source document or worksheet that supports the causality noted on the AE form, ensures that a medically qualified assessment of causality was done. This initialed document must be retained for the required regulatory time frame. The criteria below are intended as reference guidelines to assist the investigator in assessing the likelihood of a relationship between the test drug and the adverse event based upon the available information  The following components are to be used to assess the relationship between the Sponsor's product and the AE; the greater the correlation with the components and their respective elements (in number and/or intensity), the more likely the Sponsor's product caused the adverse event:	
	Exposure	Is there evidence that the subject was actually exposed to the Sponsor's product such as: reliable history, acceptable compliance assessment (pill count, diary, etc.), expected pharmacologic effect, or measurement of drug/metabolite in bodily specimen?
	Time Course	Did the AE follow in a reasonable temporal sequence from administration of the Sponsor's product? Is the time of onset of the AE compatible with a drug-induced effect (applies to trials with investigational medicinal product)?
	Likely Cause	Is the AE not reasonably explained by another etiology such as underlying disease, other drug(s)/vaccine(s), or other host or environmental factors

Relationship to Sponsor's Product (continued)	The following components are to be used to assess the relationship between the Sponsor's product and the AE: (continued)	
	Dechallenge	Was the Sponsor's product discontinued or dose/exposure/frequency reduced? If yes, did the AE resolve or improve? If yes, this is a positive dechallenge. If no, this is a negative dechallenge. (Note: This criterion is not applicable if: (1) the AE resulted in death or permanent disability; (2) the AE resolved/improved despite continuation of the Sponsor's product; (3) the trial is a single-dose drug trial); or (4) Sponsor's product(s) is/are only used one time.)
	Rechallenge	Was the subject re-exposed to the Sponsor's product in this trial? If yes, did the AE recur or worsen? If yes, this is a positive rechallenge. If no, this is a negative rechallenge. (Note: This criterion is not applicable if: (1) the initial AE resulted in death or permanent disability, or (2) the trial is a single-dose drug trial); or (3) Sponsor's product(s) is/are used only one time.) NOTE: IF A RECHALLENGE IS PLANNED FOR AN ADVERSE EVENT WHICH WAS SERIOUS AND WHICH MAY HAVE BEEN CAUSED BY THE SPONSOR'S PRODUCT, OR IF RE-EXPOSURE TO THE SPONSOR'S PRODUCT POSES ADDITIONAL POTENTIAL SIGNIFICANT RISK TO THE SUBJECT THEN THE RECHALLENGE MUST BE APPROVED IN ADVANCE BY THE SPONSOR CLINICAL DIRECTOR AND THE INSTITUTIONAL REVIEW BOARD/INDEPENDENT ETHICS COMMITTEE.
	Consistency with Trial Treatment Profile	Is the clinical/pathological presentation of the AE consistent with previous knowledge regarding the Sponsor's product or drug class pharmacology or toxicology?
The assessment of relationship will be reported on the case report forms /worksheets by an investigator who is a qualified physician according to his/her best clinical judgment, including consideration of the above elements.		
Record one of the following:	Use the following scale of criteria as guidance (not all criteria must be present to be indicative of a Sponsor's product relationship).	
Yes, there is a reasonable possibility of Sponsor's product relationship.	There is evidence of exposure to the Sponsor's product. The temporal sequence of the AE onset relative to the administration of the Sponsor's product is reasonable. The AE is more likely explained by the Sponsor's product than by another cause.	
No, there is not a reasonable possibility of Sponsor's product relationship	Subject did not receive the Sponsor's product OR temporal sequence of the AE onset relative to administration of the Sponsor's product is not reasonable OR the AE is more likely explained by another cause than the Sponsor's product. (Also entered for a subject with overdose without an associated AE.)	

## 7.2.4 Sponsor Responsibility for Reporting Adverse Events

All Adverse Events will be reported to regulatory authorities, IRB/IECs and investigators in accordance with all applicable global laws and regulations, i.e., per ICH Topic E6 (R1) Guidelines for Good Clinical Practice.

# 8.0 STATISTICAL ANALYSIS PLAN

## 8.1 Statistical Analysis Plan Summary

This section contains a brief summary of the statistical analyses for this trial. Full detail is in the statistical analysis plan (SAP) (Section 8.2).

### 8.1.1 Statistical Methods

#### 8.1.1.1 Safety

Summary statistics and plots will be generated for the change from baseline values at the interim analysis and the end of study, as deemed clinically appropriate. Depending on the safety parameter, the difference from baseline will either be computed on the original scale (raw change from baseline) or on the log-scale and back-transformed for reporting (percent change from baseline). Summary statistics for the raw laboratory safety tests, ECGs, and/or vital signs may also be computed, as deemed clinically appropriate.

#### 8.1.1.2 Pharmacokinetics

### IV Administration (Group 1 Cohorts 1 and 2, Group 2, and Group 3)

A non-model based geometric mean of the AUC and  $C_{max}$  of tedizolid phosphate and its active metabolite, tedizolid, after administration (5th dose or first dose on Day 3 for multiple-dose groups) will be calculated for each PK sampling scheme by age and dose (if dose adjusted at interim analysis) group. A ratio of non-model-based geometric mean between two PK sampling schemes will also be calculated by age group. If the ratio is greater than 2.0 or less than 0.5 for an age group, the naïve-pooled approach will be used to summarize the PK. In this approach, only one value for each PK parameter will be estimated for each age group, as specified in Section 7.1.3.2.1. If the ratio of non-model based geometric mean between two PK sampling schemes is within 0.5 and 2.0 for an age group, individual PK parameter values will be estimated. And an analysis of variance (ANOVA) model including factor for Group/Cohort will be used to analyze log transformed PK parameter values of tedizolid phosphate and tedizolid. Point estimates and two-sided 95% confidence intervals will be constructed for the geometric mean (GM) in pediatric subjects by Group/Cohort of AUC and  $C_{max}$  of tedizolid phosphate and tedizolid.

### Oral Administration (Groups 4, 5 and 6)

The AUC of tedizolid phosphate and tedizolid, administered as oral suspension will be calculated using naïve-pooled approach as specified in Section 7.1.3.2.1. Only one value for AUC will be estimated for each age group.

The bioavailability will be estimated by dividing the naïve-pooled AUC from oral administrated subjects by the estimated AUC from IV administrated subjects, for each age

group. If the ratio of non-model based GM between two PK sampling schemes is between 0.5 and 2.0, then GM AUC estimate from ANOVA model will be used as the estimated AUC from IV administrated subjects. Otherwise, the naïve-pooled AUC estimate from each age group will be used. An average bioavailability will also be reported across age groups.

For IV administrated subjects with available individual PK parameter estimates, individual values will be listed for each PK parameter by age group, dose and PK sampling scheme, and the following (non-model-based) descriptive statistics will be provided: N (number of subjects with non-missing data), arithmetic mean, standard deviation, arithmetic percent CV (calculated as  $100 \times \text{standard deviation}/\text{arithmetic mean}$ ), median, minimum, maximum, GM, and geometric percent CV (calculated as  $100 \times \text{sqrt}[\exp(s^2) - 1]$ , where  $s^2$  is the observed variance on the natural log-scale).

The effects of body weight and renal function on the PK parameter values may be graphically analyzed if appropriate. These data may be used in a population PK analysis.

### **8.1.1.3 Power**

See Section 8.2.7.

## **8.2 Statistical Analysis Plan**

The statistical analysis of the data obtained from this study will be conducted by, or under the direct auspices of, the Early Clinical Development Statistics Department in collaboration with the Quantitative Pharmacology and Pharmacometrics Department and Translational Pharmacology Department of the Sponsor.

If, after the study has begun, changes are made to the statistical analysis plan stated below, then these deviations to the plan will be listed, along with an explanation as to why they occurred, in the Clinical Study Report.

### **8.2.1 Hypotheses**

This is a descriptive, non-comparative study and no hypothesis testing is planned.

### **8.2.2 Analysis Endpoints**

For all analyses, baseline is defined as the most recent measurement prior to the first administration of trial drug, unless otherwise specified.

#### Primary Endpoints

Pharmacokinetics: The pharmacokinetic variables for tedizolid phosphate and tedizolid (AUC0-last, AUC0-inf, Cmax, Tmax, apparent terminal t1/2) are of interest.

#### Secondary Endpoints:

Safety: safety endpoints will include all types of adverse experiences, in addition to laboratory safety tests, and vital signs.

#### Exploratory Endpoints

Pharmacokinetics: bioavailability of tedizolid following administration of tedizolid phosphate oral suspension (Part B, Groups 4, 5 and 6).

The PK parameters are defined as follows:

AUC 0-last	Area under the concentration-time curve from time 0 to time of last quantifiable drug concentration
AUC 0-∞	Area under the concentration-time curve from time 0 extrapolated to infinity
CL or CL/F	Total body clearance or apparent total body clearance
Vd or Vd/F	Volume of distribution or apparent volume of distribution
C max	Maximum concentration
T max	Time to reach C max
t 1/2	(Apparent terminal) Half-life
%BA	Percent bioavailability (oral only) calculated as (individual AUC 0-inf PO * dose IV) / (mean AUC 0-inf IV * dose PO) (for similar collection scheme), and overall for mean across both collection schemes, within and across all age groups

### 8.2.3 Approaches to Analyses

The following populations are defined for the analysis and reporting of data. All subjects will be reported, and their data analyzed, according to the treatment(s) they actually received.

*All Subjects as Treated (ASaT)* - All subjects who received at least one dose of the investigational drug. This population will be used for assessments of safety and tolerability.

*Per-Protocol (PP)* – The set of data generated by the subset of subjects who comply with the protocol sufficiently to ensure that these data will be likely to exhibit the effects of treatment, according to the underlying scientific model. Compliance covers such considerations as exposure to treatment, availability of measurements and absence of important protocol deviations. Important protocol deviations will be identified to the extent possible by individuals responsible for data collection/compliance, and its analysis and interpretation. Any subjects or data values excluded from analysis will be identified, along with their reason for exclusion, in the CSR. At the end of the study, all subjects who are compliant with the study procedure as aforementioned and have valid samples collected for at least 2 of the assigned 3 time points will be included in the primary analysis dataset. This population will be used for the PK analyses.

### 8.2.4 Statistical Methods

#### 8.2.4.1 Analysis Overview

All references within this data analysis section to the log transformation or log function pertain to the natural log. If log transformation is used, the confidence intervals for the means (mean differences) will be constructed on the natural log-scale and will reference the t-distribution. Exponentiating the least-squares means (mean differences) and lower and upper limits of these confidence intervals will yield estimates for the population geometric means

(population geometric mean ratios) and confidence intervals about the geometric means (geometric mean ratios) on the original scale.

Data will be examined for departures from the assumptions of the statistical model(s) as appropriate; eg, heteroscedasticity, non-normality of the error terms. Distribution-free methods may be used if a serious departure from the assumptions of the models(s) is observed, or suitable data transformations may be applied.

#### **8.2.4.2 Safety**

Summary statistics and plots will be generated for the change from baseline values at the interim analysis and the end of study, as deemed clinically appropriate. Depending on the safety parameter, the difference from baseline will either be computed on the original scale (raw change from baseline) or on the log-scale and back-transformed for reporting (percent change from baseline). Summary statistics for the raw laboratory safety tests, ECGs, and/or vital signs may also be computed, as deemed clinically appropriate.

#### **8.2.4.3 Pharmacokinetics**

Concentrations of tedizolid phosphate and tedizolid will be imputed as zero at time zero, where no samples were collected. Any missing postdose plasma concentrations will be treated as missing. Values below the limit of quantification (BLOQ) will be assigned a value of zero. For summary statistics of plasma concentration versus time data, at least half of the values at that timepoint must be  $>0$  in order to report a value at that timepoint. At least 2 quantifiable postdose values are required for calculation of individual pharmacokinetics. AUC will be calculated using linear up/log down trapezoidal rule.

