### 3.0 OBJECTIVE(S) & HYPOTHESIS(ES)

#### 3.1 Primary Objective(s) & Hypothesis(es)

##### Part A

1. Primary Objective: To describe the single-dose pharmacokinetics (PK) of IV tedizolid phosphate and its active metabolite, tedizolid, when administered to pediatric subjects, aged 28 days to <24 months (Group 1 [Cohorts 1 and 2 combined]), full-term neonatesa aged birth to <28 days (Group 2), and preterm neonatesb aged birth to <28 days (Group 3).
2. Primary Objective: To describe the multiple-dose PK of IV tedizolid phosphate and its active metabolite, tedizolid, when administered to full-term neonatesa aged birth to <28 days (Group 2), and preterm neonatesb aged birth to <28 days (Group 3).

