#### **4.1.1 Pharmaceutical and Therapeutic Background**

Tedizolid phosphate (SIVEXTRO®, MK-1986) is a novel oxazolidinone prodrug antibiotic that is rapidly converted in vivo by phosphatases to the microbiologically active moiety tedizolid. Tedizolid is a protein synthesis inhibitor that interacts with the 50S subunit of the bacterial ribosome. Tedizolid has bacteriostatic activity against gram-positive bacteria including common skin pathogens *Staphylococcus aureus* (both methicillin-sensitive and –resistant strains) and *Streptococcus pyogenes*, less common species causing acute bacterial skin and skin structure infections (ABSSSI), *S. anginosus*-milleri group and *Enterococcus faecalis*, and other gram-positive aerobes and anaerobes. The tablet is highly (~90%) bioavailable after oral dosing in adults, and is provided in both IV and oral formulations. Following oral administration of a single 200 mg dose to healthy adults, maximal plasma concentrations of tedizolid (approximately 2 µg/mL) are achieved approximately 3 hours after dosing when fasted; Tmax is delayed by approximately 6 hours when tedizolid phosphate is dosed with a meal; however, the AUC is unaffected by administration with or without food. Conversion of the prodrug tedizolid phosphate to the active metabolite, tedizolid, is extremely rapid, with a half-life of 10 minutes. When the drug is dosed IV, exposure peaks at the end of the 60-minute infusion period. Systemic prodrug is rarely detectable after oral dosing. The terminal half-life of tedizolid elimination is 12 hours. Exposure is generally dose-proportional in humans.

Tedizolid phosphate is approved for the treatment of ABSSSI in adults in multiple regions, including the United States and European Union (EU), but its safety and effectiveness have not been established in children and adolescents.

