## **5.3 Randomization or Treatment Allocation**

During the course of the study, subjects will be assigned non-randomly to one of 2 different treatment routes (IV or orally) and to a specific PK sampling scheme. Treatment allocation will be controlled, and the PK sampling scheme will be assigned via IRT.

After the documented informed consent form is provided by the parent/guardian/LAR and study eligibility is confirmed, designated site study staff will obtain the subject's treatment allocation number and trial drug assignment from a computer-generated allocation code via IRT. Subjects enrolled in the study will be assigned the treatment and PK sampling scheme corresponding to the next available allocation number in the computer-generated schedule.

Treatment allocation will occur centrally using IRT. There are 6 treatment Groups (Group 1 is split into Cohorts 1 and 2 for the purposes of enrollment only). Within each Group, subjects will be assigned to one of two PK sampling schema, as described in Section 7.1.3.2.2. Subjects will be assigned non-randomly to tedizolid phosphate IV or oral suspension as follows:

Group 1 (N=10):

- Cohort 1 (n=4-6): MK-1986 IV single-dose given to pediatric subjects aged 28 days to  $<6$  months.
- Cohort 2 (n=4-6): MK-1986 IV single-dose given to pediatric subjects aged 6 months to  $<24$  months.

Group 2 (N=10):

- Cohort 1 (n=6): MK-1986 IV single-dose given to full-term neonates\* aged birth to  $<28$  days
- Cohort 2 (n=4): MK-1986 IV multiple-dose (twice daily for 3 days) given to full-term neonates\* aged birth to  $<28$  days

Group 3 (N=10):

- Cohort 1 (n=6): MK-1986 IV single-dose given to preterm neonates† aged birth to  $<28$  days
- Cohort 2 (n=4): MK-1986 IV multiple-dose (twice daily for 3 days) given to preterm neonates† aged birth to  $<28$  days

Group 4 (N=4): MK-1986 oral suspension single-dose given to pediatric subjects aged 28 days to <24 months,

Group 5 (N=4): MK-1986 oral suspension single-dose given to full-term neonates\* aged birth to <28 days, and

Group 6 (N=4): MK-1986 oral suspension single-dose given to preterm neonates† aged birth to <28 days.

In subjects who receive multiple-dose study medication, tedizolid phosphate will be administered twice daily for 3 days.

Further local restrictions on cohort opening may be applied based on country-specific requirements or site constraints.

\* Full-term neonate is defined as an infant born  $\geq 37^{\text{th}}$  week of gestation.

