#### 7.1.3.2.2 Samples

In Part A, blood samples for analysis of tedizolid phosphate and tedizolid will be collected at the following timepoints ([Figure 2](#) or [Figure 3](#)) for subjects allocated to 1 of 2 collection schemes:

Subjects who receive single-dose tedizolid phosphate IV (shown graphically in [Figure 2](#)):

1. immediately after the end of the 1-hour infusion, and at 3 and 12 hours after the start of infusion

OR

2. at 1.5, 6, and 24 hours after the start of infusion

Subjects who receive multiple-dose tedizolid phosphate IV (shown graphically in [Figure 3](#)):

1. Day 3 at end of infusion (5th dose), 3 hours after the start of the 5th infusion, and 12 hours after the start of the 5th infusion (prior to 6th dose)

OR

2. Day 3 at 12 hours after the start of the 4th infusion (prior to 5th dose), 1.5 hours after the start of the 5th infusion, and 6 hours after the start of the 5th infusion

In Part B, blood samples for analysis of tedizolid phosphate and tedizolid will be collected at the following timepoints ([Figure 4](#)) for subjects allocated to 1 of 2 collection schemes:

Subjects who receive single-dose tedizolid phosphate oral suspension (shown graphically in [Figure 4](#)):

[figure not shown]
1. at 1, 5, and 12 hours postdose

OR

2. at 3, 8, and 24 hours postdose

[figure not shown]
[Figure 2](#), [Figure 3](#), and [Figure 4](#) provide the allowed windows for collection of blood samples.

Figure 2 Pharmacokinetic Sampling Schemes for Subjects Who Receive Single-dose Tedizolid Phosphate IV

[figure not shown]
h=hour; IV=intravenous; min=minute(s); PK=pharmacokinetics

Figure 3 Pharmacokinetic Sampling Schemes for Subjects Who Receive Multiple-dose Tedizolid Phosphate

h=hour; IV=intravenous; min=minute(s); PK=pharmacokinetics

Figure 4 Pharmacokinetic Sampling Schemes for Subjects Who Receive Single-dose Tedizolid Phosphate Oral Suspension

h=hour; min=minutes; PK=pharmacokinetics; PO=oral

Note: PK samples will not be collected from subjects receiving oral suspension who vomit during and/or within 90 minutes after administration of a dose.

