### **8.2.7 Sample Size and Power Calculations**

#### Pharmacokinetics:

It is assumed that the variabilities of AUC and volume of distribution [Vd] of pediatric subjects are the same as those of adults as observed in pooled historical adult subjects from Studies MK-1986-008 (TR701-107) and MK-1986-031 (TR701-123).

Assuming the between-subject standard deviations of  $\log(AUC)$  are 0.27 and 0.32 for tedizolid phosphate and tedizolid, respectively, with 10 completers in Group 1 (Cohort 1 and Cohort 2 combined), there are 99% and 97% probabilities that the 95% CI of GM is within 60% and 140% of the GM estimate; with 6 completers in Group 2 Cohort 1, there are 78% and 58% probabilities that the 95% CI of GM is within 60% and 140% of the GM estimate.

Assuming the between-subject standard deviations of  $\log(Vd)$  are 0.28 and 0.29 for tedizolid phosphate and tedizolid, respectively, with 10 completers in Group 1 (Cohort 1 and Cohort 2 combined), there are 99% and 99% probabilities that the 95% CI of GM is within 60% and 140% of the GM estimate; with 6 completers in Group 2 Cohort 1, there are 74% and 70% probabilities that the 95% CI of GM is within 60% and 140% of the GM estimate.

Power calculations are not provided for subjects who receive multiple doses of tedizolid phosphate; the sample size was based on pragmatic considerations.

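### The rule of two quantifiable values drops valid tedizolid phosphate Cmax values according to concentration, and can leave the scheme-ratio switch undefined

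*Combined protocol and SAP*

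**What the plan says.** The first primary objective for Part A (section 3.1) is "To describe the single-dose pharmacokinetics (PK) of IV tedizolid phosphate and its active metabolite, tedizolid, when administered to pediatric subjects" in three age groups. Section 8.2.2 lists Cmax, AUC, Tmax and half-life of both analytes as primary endpoints.

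Section 7.1.3.2.2 gives each single-dose IV subject three samples. Scheme 1 is "immediately after the end of the 1-hour infusion, and at 3 and 12 hours after the start of infusion"; Scheme 2 is "at 1.5, 6, and 24 hours after the start of infusion". Section 5.3 states "Within each Group, subjects will be assigned to one of two PK sampling schema" and does not give the split. The multiple-dose cohorts keep the same gap in Scheme 1: end of infusion, then 3 h, then 12 h.

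Section 4.1.1 states "Conversion of the prodrug tedizolid phosphate to the active metabolite, tedizolid, is extremely rapid, with a half-life of 10 minutes".

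Section 8.2.4.3 states "Values below the limit of quantification (BLOQ) will be assigned a value of zero" and "At least 2 quantifiable postdose values are required for calculation of individual pharmacokinetics". It then asks for geometric means of AUC and Cmax of both analytes by sampling scheme, and for the ratio of the two schemes. A ratio outside 0.5 to 2.0 leads to naïve pooling. A ratio inside that range leads to individual values, an ANOVA and 95% confidence intervals. Section 7.1.3.2.1 also permits naïve pooling for Groups 1-3 but does not require it.

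**The concern.** A two-value minimum is sensible for a quantity that needs a slope or an area. Cmax is a single observed concentration. For a prodrug that is nearly gone within an hour of the infusion ending, the second quantifiable value exists only in subjects whose conversion is slow or whose concentrations are high. The rule therefore removes subjects because of the outcome being summarised, and the confidence interval cannot reflect the missing low values.

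Two things are at stake. The prodrug Cmax geometric mean, a primary endpoint, may describe a selected part of each age group. If conversion speed differs with age, the amount of selection differs too, which could resemble an age trend. In addition, the switch between individual and pooled summaries needs a geometric mean from each scheme, and the same rule may leave one scheme with none.

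**Working it through.** **Inputs from the documents.** Half-life 10 min (4.1.1, background section); 1-h infusion and sampling times (7.1.3.2.2); between-subject SDs for the prodrug of 0.27 for log AUC and 0.28 for log Vd (8.2.7).

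**Assumptions not in the documents.** One compartment; CL-Vd correlation 0 or 0.5; assay limit L = median end-of-infusion concentration / R, with R from 100 to 10,000; infant half-lives of 15, 20 and 30 min as sensitivity cases; equal split between schemes.

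**The plan's own figures.** Section 8.2.7 says the SDs of log AUC "are 0.27 and 0.32 for tedizolid phosphate and tedizolid, respectively, with 10 completers in Group 1". Computing P(t(0.975, n−1)·s/√n ≤ ln 1.4) with (n−1)s²/SD² distributed as chi-square reproduces the stated precision. For AUC (prodrug/tedizolid) it gives 99.9%/97.8% at n = 10 and 78.3%/58.7% at n = 6, against 99%/97% and 78%/58%. The Vd figures also reproduce. All assume that every completer contributes.

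**Decay after the infusion, half-life 10 min.** Fraction remaining = 2^(−minutes/10):
- 1.5 h: 2^(−3) = 1/8
- 3 h: 2^(−12) = 1/4,096
- 6 h: 2^(−30), about 1e-9

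A typical Scheme 1 subject has a second quantifiable value only if L is below about 1/4,096 of the end-of-infusion level. A typical Scheme 2 subject has one quantifiable value and is dropped.

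**Simulation (400,000 subjects per case).** k = CL/V, C_end = (rate/CL)(1 − e^(−k)), C(t) = C_end·e^(−k(t−1)). A Scheme 1 subject is retained if C_end and C(3) both exceed L. Error = geometric mean in retained / geometric mean in all. Ranges cover correlation 0 and 0.5, at 10 min:

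| R | Scheme 1 retained | Cmax error | None of 5 Scheme 1 subjects retained |
|---|---|---|---|
| 100 | 2-8% | ×1.31-1.34 | 66-89% |
| 1,000 | 26-33% | ×1.17-1.19 | 14-22% |
| 10,000 | 60-64% | ×1.08-1.11 | about 1% |

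The largest Cmax error over the same R falls to about 14% at 15 min, 6.5% at 20 min and 1% at 30 min.

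**Scheme 2.** At 10 min at most 2.1% are retained. With five subjects the chance that none is retained is at least (1 − 0.021)^5 = 0.90. The scheme ratio then has no second term.

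**AUC.** The planned linear-up/log-down rule starts at zero and has no sample during the infusion. At 10 min, k = 0.693/(1/6) = 4.16 per h and C_end = 0.984/CL per unit dose. The triangle is 0.5 × 0.984 = 0.492 and the tail is 0.984/4.16 = 0.237, which sum to 0.73 of the true value (1/CL) with nobody dropped. Applying that rule to the retained Scheme 1 subjects and dividing by the true geometric mean in everyone gives 1.25-1.26 at R = 100, 0.96-1.01 at R = 1,000 and 0.83-0.88 at R = 10,000.

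**The case against.** The strongest reply is that the plan already has a safeguard. If Cmax were formed from each subject's first sample with nobody dropped, the scheme ratio would be 8.7-9.4 at 10 min, 4.2-4.5 at 15 min and 2.9-3.1 at 20 min. All exceed 2.0, so pooling would follow. This does not rescue the text as written, because the two-value rule filters the individual values before the ratio is taken. At 10 min Scheme 2 is then usually empty. The plan does not cover that case, while per-scheme and descriptive geometric means of whatever individual values exist are still requested.

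A reader might infer that the prodrug AUC geometric mean is also biased upward. The documents do not support that. Selection does push AUC up, but the trapezoid's understatement during the infusion pushes it down, and the net error runs from below to above the truth depending on the assay limit. A reader might also infer that only slow converters remain. That is too strong for Scheme 1, where 60-64% are retained with a sensitive assay.

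Three further replies stand in part. The size rests on an assay limit and an infant half-life that the documents do not give. Section 8.2.3 already promises to identify exclusions and reasons in the study report. The plan treats AUC as the predictor of efficacy and tedizolid as the active moiety. With a 12-hour half-life tedizolid barely feels the rule, so the consequence for dose selection is small.

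**Conclusion.** The concern holds for prodrug Cmax and for the undefined ratio. The rule makes inclusion depend on concentration, so the Scheme 1 tedizolid phosphate Cmax geometric mean is selected upward or not estimable. At a 10-minute half-life the error is +8% to +34% over the assumed assay limits (+17% to +19% at 1/1,000). At the coarsest limit, having no evaluable Scheme 1 subject is the likelier result. With slower conversion the error fades: at most about 14% at 15 minutes, about 6.5% at 20 and about 1% at 30.

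Individual prodrug AUC and half-life are also selected on exposure, but the net direction of the AUC error is not established. The point concerns a primary-endpoint analyte and should be settled before the final analysis. It does not touch the active metabolite to any material degree.

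**What to change.** In section 8.2.4.3 of the SAP:
- Limit the two-quantifiable-value condition to parameters that need more than one concentration: AUC, half-life, CL and Vd.
- Report tedizolid phosphate Cmax from the end-of-infusion sample of every Scheme 1 subject, whether or not later samples are quantifiable. Do not combine it with Scheme 2, whose first sample is 30 minutes after the infusion. With an equal split and a ratio near 9, a combined geometric mean would be about 1/√9, or one third, of the end-of-infusion value.
- State that the naïve-pooled summary is used when a scheme has no evaluable subjects and the ratio cannot be formed.
- Label any individual prodrug AUC, half-life, CL or Vd summary as conditional on a quantifiable later sample, and give beside it the number dropped for values below the limit. State the assay limit.
- Do not present the pooled linear-up prodrug AUC as unbiased. At 10 minutes it is roughly 27% low, so either note this or use the population PK analysis that the plan already allows.

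The cost is wording only, with no new samples or subjects. The downside is that prodrug Cmax rests on Scheme 1 subjects alone, and prodrug AUC may be one pooled value per age group without a t-interval.
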